6. DEFINITIONS AND GENERAL METHODOLOGY

6.1 Enrolment date

The first date of administration of any study drug (i.e., MOR00208 or LEN).

6.2 Study drug and study treatment

Study treatment refers to MOR00208 in combination with LEN. Study drug refers to the individual drugs: MOR00208 or LEN.

6.3 Study drug administration

6.3.1 Date of first administration of study drug

The date of first administration of study drug is the first date when a non-zero dose of study drug is administered and is referred as “start date of study drug”. Start date of study drug is defined for each drug which is part of study treatment.

6.3.2 Date of last administration of study drug

The date of last administration of study drug (“last date of study drug”) is the last date when a non-zero dose of study drug is administered.

Last date of study drug is defined for each drug which is part of study treatment.

6.3.3 Date of first administration of study treatment

The date of first administration of study treatment (“start date of study treatment”) is the first date when a non-zero dose of any component of study treatment is administered.

For example: if the 1st dose of MOR00208 is taken on 03JAN2017, and 1st dose of LEN is taken on 05JAN2018, then the “Start date of study treatment” is 03JAN2017.

6.3.4 Date of last administration of study treatment

The date of last administration of study treatment (“last date of study treatment”) is the last date when a non-zero dose of any component of study treatment is administered.

For example: if the last dose of MOR00208 is taken on 13APR2017, and last dose of LEN is taken on 20APR2018, then the “Last date of study treatment” is 20APR2018.

6.4 Reference start date and study day

The reference start date **for all safety assessments** (e.g. adverse event onset, laboratory abnormality occurrence, vital sign measurement, dose interruption etc.) will be the start date of study treatment.

The reference start date **for all efficacy assessments** (e.g. tumour assessment, death, ECOG performance status) will be the start date of study treatment.

For **any non-safety screening assessments** or events such as baseline disease characteristics or medical history (e.g., time since diagnosis of disease) that occurred prior to start date of study treatment the reference start date will be the start date of study treatment.

The study day describes the day of the event or assessment date, relative to the reference start date (i.e., the study treatment).

The reference start date is designated as Study Day 1. Study Day –1 is the day that precedes Study Day 1. Study Day 0 is not defined.

The study day will be calculated as:

- The date of the event (visit date, onset date of an event, assessment date etc.) minus reference start date + 1 if the event is on or after the reference start date.
- The date of the event (visit date, onset date of an event, assessment date etc.) minus reference start date if the event precedes the reference start date.

The study day will be displayed in the data listings. It will not be used for numerical computations for example calculating exposure.

6.5 Screening failure

These patients are not treated. Screening failures are patients who have signed informed consent and failed screening criteria in a study. Patients who signed informed consent and fulfilled screening criteria, but have never received treatment are not considered as screening failures.

6.6 Time unit

A month-length is 30.4375 days (365.25 / 12). If duration is to be reported in months, duration in days is divided by 30.4375. If duration is to be reported in years, duration in days will be divided by 365.25.

6.7 Baseline

Baseline is the result of an investigation describing the “true” uninfluenced state of the patient, defined as the period from the date of signing any informed consent document to the start date of study treatment. Assessments, specified to be collected post-dose on the first date of treatment are not considered as baseline values.

For **efficacy evaluations**, the last non-missing assessment, including unscheduled assessments on or before the start date of study treatment will be used as “baseline” value or “baseline” assessment. In the context of baseline definition, the efficacy evaluations also include the ECOG performance status.

For **safety evaluations**, unless otherwise stated, the last available assessment, including unscheduled assessments on or before the start date of study treatment will be used as “baseline” value or “baseline” assessment.

If patients have no value as defined above, the baseline result will be missing.

6.8 On treatment assessment/event

An **on-treatment assessment/event** is defined as any assessment/event happening after the start date of study treatment, i.e. assessments/events happening in the following time interval (including the lower and upper limits): start date of study treatment + 1; last date of study treatment + 30 days.

Assessments collected post-dose on the start date of study treatment are on-treatment assessments. Data listings will include all assessments/events, flagging those which are not on-treatment assessments/events.

A **post-treatment assessment/event** is defined as any assessment/event happening after the completion of on-treatment phase, that is assessments/events happening in the

following time interval (including the lower and upper limits): date of last administration of study treatment + 30 days + 1; Date of Study Discontinuation.

6.9 Start and end date for time to event variables

Assessment date

For each assessment (i.e. evaluation number), the **assessment date** is calculated as the latest of all measurement dates (e.g. X-ray, CT-scan) if the overall response at that assessment is CR/PR/SD/UNK/NE.

Otherwise - if overall response is progression – the assessment date is calculated as the earliest date of all measurement dates at that evaluation number.

Start dates

For all “time to event” variables, other than duration of response, the start date of study treatment will be used as the start date.

For the calculation of duration of response the following start date should be used:

Date of first documented response is the assessment date of the first overall response of CR or PR.

End dates

The end dates which are used to calculate ‘time to event’ variables are defined as follows:

- Date of death (during treatment as recorded on the treatment completion page or during follow-up as recorded on the study evaluation completion page or the survival follow-up page).
- Date of progression is the first assessment date at which the overall response was recorded as progressive disease.
- When there is no documentation of radiologic evidence of progression, and the patient discontinued for ‘Disease progression’ due to documented clinical deterioration of disease, the date of discontinuation is used as date of progression.
- If no post-baseline assessments are available (before an event or a censoring reason occurred) the start date of study treatment is used as the end date.

Calculation of ‘time to event’ variables

Time to event = End Date - Start date + 1 (in days).

When no post-baseline tumor assessments are available, the start date of study treatment will be used as end date (duration = 1 day).

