10.6.2.2 Duration of Response (DoR) and Time to Next Treatment (TTNT)

DoR is defined as the time interval between the initial time point of tumour response (CR or PR whichever status is recorded first) and the first date that recurrence of progressive disease is documented. Response duration by the local and central assessment will be tabulated with descriptive statistics.

Disease progression is defined as the first occurrence of progressive disease according to the revised response criteria ([Cheson et al., 2007](#)) as assessed by central radiology / clinical readers.

TTNT is defined as the time from study entry (= first dosing) to the institution of next therapy for any reason including disease progression, treatment toxicity and patient preference. TTNT will be descriptively analysed.

10.6.2.3 Time to Event Variables: Progression-Free Survival (PFS), Overall Survival (OS), and Time to Progression (TTP)

PFS is defined as the time elapsed between study entry (= first dosing) and lymphoma progression or death from any cause, whichever occurs first. Patients not experiencing a lymphoma progression or death from any cause will be censored at the last available tumour assessment. The same holds true for patients who are lost-to-follow-up.

OS is defined as time from study entry (= first dosing) until the date of death from any cause. Patients who are alive but have dropped out early will be censored at the time of the last available study visit assessment.

TTP is defined as the time from study entry (= first dosing) until documented lymphoma progression or death as a result of lymphoma. The events of interest are only disease progression and death from lymphoma. Death from other causes will not be taken into account (will be censored) in the TTP evaluation. Patients not experiencing progressive disease will be censored at the last NHL assessment. Deaths from other causes will be censored at the time of death. Early drop-outs without any documented date of progression will be censored at the time of the last NHL assessment.

Kaplan-Meier methodology will be used to evaluate median survival, presenting corresponding statistical parameters and Kaplan-Meier survival curves. Further analyses concerning influence of IPI and GC/non-GC B-cells will be specified in the SAP.

TTP will be compared to the TTP of the patients' most recent therapy by tabulating descriptive statistics (including 95% confidence limits).

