6.14.2 Disease progression

Only objective progressive disease (PD) according to the Cheson criteria as mentioned in Table 3 is considered in all efficacy analyses.

In particular, discontinuation due to PD (from the "End of Treatment Completion" eCRF page), without supporting objective evidence (as defined above), will not be considered as PD in the determination of best overall response rate (ORR) and in the analysis for progression-free survival (PFS).

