10.2.2 Endpoint: Progression-free survival

PFS will be defined as the time (in months) from the date of the first administration of any study drug to the date of tumour progression or death from any cause (see Independent Review Charter version 4.3, 10-JUL-2018). The date of progression will be the first date for which progressive disease was assessed as the objective response. The tumour assessments will be derived according to the IWG treatment response criteria for malignant lymphoma (Cheson et al., 2007; see section 6.14), by an Independent Radiology/Clinical Review Committee (IRC). The review process will be defined in the IRC Charter.

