**Table 13: Censoring Rules**

Situation	Date of Progression or Censoring	Outcome	Censoring reason
Ongoing and No event until data cut-off	Date of last adequate tumour assessment	Censored	Ongoing
Discontinued the study with no event	Date of last adequate tumour assessment	Censored	Discontinued without event
No baseline tumour assessment	Date of C1D1	Censored	No baseline tumour assessment
Lost to follow-up	Date of last IRC tumour assessment (or C1D1 in case of study discontinuation w/o progression before any post-baseline assessment)	Censored	Lost to follow-up
Patient received non-study anti-DLBCL treatment before disease progression	Date of last adequate tumour assessment before start of non-study cancer treatment	Censored	New anti-cancer therapy started
Clinical Progression*	Date of last adequate tumour assessment	Censored for Analysis based on Investigator assessment only	Clinical Progression not validated by Cheson Criteria
PD by modality not including PET Scan is not confirmed by modality including PET Scan**.	Date of last adequate tumour assessment	Censored for Analysis based on Investigator assessment only	Non-PET PD not confirmed by PET.
Death before any date of PD assessment	Date of death	Progressed	
Death between adequate assessments	Date of death	Progressed	
Death or progression after two or more	Date of last adequate	Censored	Event documented

STATISTICAL ANALYSIS PLAN

 MorphoSys AG
 MOR208C203

Situation	Date of Progression or Censoring	Outcome	Censoring reason
missed visits	tumour assessment		after two or more missing tumor assessments
EOT after two or more missed assessments without disease progression	Date of Last adequate Tumour Assessment	Censored	Adequate assessment no longer available

Abbreviations: EOT = End of Treatment; IRC = Independent Review Committee; PD = progressive disease; CT = Computed tomography; PET = Positron emission tomography. *Progression as per Investigator's assessment and without meeting PD criteria according to Response Criteria for Malignant Lymphoma (Cheson et al., 2007). **The rule only applies in case a PET-including modality is performed after a non-PET including modality.

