10.2.6 Sensitivity analyses

- The main analysis as described in Section 10.2.5 will be conducted on the PPS.
- The main analysis as described in Section 10.2.5 will be conducted based on the INV response assessment as entered on the 'Lymphoma Tumour Assessment' eCRF page. The same censoring rules will apply as for the analysis based on the IRC assessment. If the response assessment is not based on radiological examination the date when the diagnosis of relapse or progression was made by the investigator is considered as the date of progression. The analysis will be conducted using both the FAS and the PPS.
- Patients having more than one missed visit, but having an available death date, will be included in the time-to-event analysis and considered as having a PFS event. The analysis will be performed on the FAS for both IRC and INV response assessment.

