10.5.2 Endpoint: Time to progression

TTP is defined as the time from the first administration of any study drug until documented DLBCL progression or death as a result of lymphoma. Death from other causes than lymphoma will not be considered in relation to the TTP evaluation.

If a patient does not have an event, TTP will be censored on the date of the last tumour assessment before the data analysis cut-off date or the anti-neoplastic therapy start date if the patient started any new anti-neoplastic therapy or the date of death for death from other causes than lymphoma.

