16.4.2 Event-free survival

A Kaplan-Meier analysis for event-free survival (EFS) will be performed using the FAS based on the IRC response assessment. The same rules definitions and analysis rules as defined in Section 10.2 will be applied, with the following exception:

The initiation of a new anti-DLBCL therapy (medication, radiation, surgery) will be considered as an EFS event, instead of leading to censoring.

A Kaplan-Meier curve will be produced for illustration.

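### SAP 6.9 counts clinical deterioration without scan evidence as progression, SAP 6.14.2 and Table 13 do not, and nothing says which rule governs PFS, DoR, TTP and EFS

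*SAP*

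**What the plan says.** SAP 6.9 lists the end dates for calculating time-to-event variables. One bullet covers the patient with no radiologic evidence who discontinued for disease progression "due to documented clinical deterioration of disease, the date of discontinuation is used as date of progression". It is not limited to an endpoint, to the independent review (IRC) or investigator (INV) assessment, or to a sensitivity analysis.

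SAP 6.14.2 takes the contrary position: "Only objective progressive disease (PD) according to the Cheson criteria as mentioned in Table 3 is considered in all efficacy analyses". It then names discontinuation for progression without objective support and excludes it from ORR and PFS.

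Other places that bear on the same patient:
- SAP 10.2.2 (PFS): "The date of progression will be the first date for which progressive disease was assessed as the objective response".
- SAP Table 13 has a clinical-progression row that censors at the last adequate assessment, with the reason "Clinical Progression not validated by Cheson Criteria". The row is marked for the INV analysis only.
- Protocol 10.6.2.2: "Disease progression is defined as the first occurrence of progressive disease according to the revised response criteria", as read centrally.
- SAP 10.3.3 (DoR) takes its censoring from Table 13.
- SAP 10.5.2 (TTP) has its own wording, "until documented DLBCL progression or death as a result of lymphoma", and does not cite Table 13.
- SAP 16.4.2 (EFS): "The same rules definitions and analysis rules as defined in Section 10.2 will be applied", except that new anti-DLBCL therapy becomes an event.
- SAP 10.2.6 (INV sensitivity analysis of PFS) keeps the same censoring rules, but where an assessment is not radiological, "the date when the diagnosis of relapse or progression was made by the investigator is considered as the date of progression".

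**The concern.** Two general rules in the same SAP section give opposite answers for one type of patient, and the SAP does not rank them. Event status and event date for PFS, DoR, TTP and EFS then depend on which paragraph the programmer follows.

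Neither choice is neutral. Patients who stop because they are deteriorating are at higher risk than those who stay, so censoring them is informative and tends to raise the PFS, DoR and TTP curves. Counting them can err the other way, because protocol 6.6.2.3 warns that tumour flare under lenalidomide can look like progression. The note to the table in SAP 20.9 says there is no progression follow-up after treatment ends, so no scheduled later scan settles these cases.

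**Working it through.** **Text comparison.** Take a patient who stops for documented clinical deterioration, with no Cheson-defined progression.

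| Source | Status | Date |
|---|---|---|
| SAP 6.9 | Event | Discontinuation |
| SAP 6.14.2 with 10.2.2 | Not progression | – |
| Table 13, INV | Censored | Last adequate assessment |
| Table 13, IRC (no dedicated row; fits the row for leaving the study without an event) | Censored | Last adequate assessment |

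TTP is not settled by its own text: a documented clinical deterioration could pass as documented progression. The 10.2.6 sentence can be read as dating non-scan progression that does meet Cheson criteria, such as marrow involvement, but it does not say so.

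**Size.** The plan states no figure to reproduce. Scan days from the protocol schedule are 57, 113, 169, 253 and 336 (C3D1, C5D1, C7D1, C10D1, C12D28), then every 84 days as an approximation to 3-monthly. Assumptions not in the documents: exponential progression with true median m, and a share f of progressions that are clinical only.

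Let λ = ln 2/(30.4375 m), let q_j = 1 − exp(−λd_j) for a scan interval of d_j days, and let S be the true progression-free proportion at the last scan before 12 months.
- Rule A (6.9): clinical cases are events when they occur and the others at the next scan. The 12-month estimate is (1 − f)S + f·S(12).
- Rule B (6.14.2/Table 13): clinical cases leave the risk set at the previous scan, or at day 1 if there is none. Each scan contributes (1 − q_j)/(1 − f·q_j), so the estimate is S/∏(1 − f·q_j).

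PFS with m = 6: the intervals are 56, 56, 56, 84 and 83 days, λ = 0.003795 per day, and q = 0.1915 (three times), 0.2730 and 0.2702. S = exp(−0.003795 × 335) = 0.280 and S(12) = 0.250.
- f = 0.10: A = 0.9 × 0.280 + 0.1 × 0.250 = 0.277; B = 0.280/0.893 = 0.314.
- f = 0.20: A = 0.8 × 0.280 + 0.2 × 0.250 = 0.274; B = 0.280/0.795 = 0.353.
- Patients among 80 whose status changes within 12 months: 80 × f × 0.75 = 6.0 at 10% and 12.0 at 20%.

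A simulation of the same set-up agrees to about 0.001. It was also run with a death before the second missed scan counted as an event, as Table 13 requires, assuming a median survival after clinical progression of 6 or 2 months:

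| 12-month rate | f | A | B | B with deaths (6 / 2 months) |
|---|---|---|---|---|
| PFS, m = 6 | 0.05 | 0.278 | 0.296 | 0.291 / 0.285 |
| PFS, m = 6 | 0.10 | 0.277 | 0.313 | 0.303 / 0.291 |
| PFS, m = 6 | 0.20 | 0.274 | 0.352 | 0.328 / 0.303 |
| PFS, m = 12 | 0.20 | 0.523 | 0.597 | 0.575 / 0.551 |
| DoR, m = 12, response at day 57 | 0.10 | 0.501 | 0.535 | 0.525 / 0.514 |
| DoR, m = 12, response at day 57 | 0.20 | 0.501 | 0.571 | 0.549 / 0.526 |

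With deaths counted, the status changes per 80 patients fall to 4.0 / 1.9 at 10% and 8.0 / 3.8 at 20%.

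Medians are a poor measure here because they sit on the scan grid. At m = 6 and f up to 0.2, the Kaplan-Meier median is 8.3 months under B and 8.0 to 8.3 under A.

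**The case against.** The strongest reply is that the intent is plain. SAP 6.14.2 names this very case, and 10.2.2, Table 13 and protocol 10.6.2.2 agree with it; one generic bullet stands alone. That is a fair reading and it decides which rule to keep. It remains an inference: the bullet sits in the section that defines end dates for programming and carries no restriction.

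A second reply is that EFS takes its rules from Section 10.2, is IRC only and counts new therapy as an event. The effect on EFS is indeed likely to be smaller. But EFS is a time-to-event variable, so 6.9 still applies to it.

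Third, other analyses already help. SAP 10.2.6 and 10.5.4 count patients with missed visits and a known death date as PFS or TTP events. SAP 20.9 turns leaving the study without an event into an event at discontinuation of the last study drug, which for IRC is close to the 6.9 date. These recover part of the group and give a pessimistic bound for PFS and DoR. None isolates this rule: 20.9 changes three rules together, omits TTP and leaves the remaining Table 13 rows as they are, which most naturally includes INV clinical progression.

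Fourth, the clinical-only share is unknown. SAP Table 12 lists an end-of-treatment scan, which could turn some cases into objective progression; protocol 7.2.14.1 is unclear on whether it is required after withdrawal for progression. This stands, and it is why the figures are illustrative. Finally, the endpoints are secondary or exploratory and carry no formal test, which limits the weight of the point.

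**Conclusion.** The contradiction is real and unresolved in the text. SAP 6.9 is wrong as written, judged against the rest of the plan, and should be corrected. Under the stated assumptions, censoring instead of counting raises 12-month PFS by about 4 points at a 10% clinical-only share (0.313 − 0.277) and 8 points at 20% (0.352 − 0.274). With early deaths counted, the gap is about 1 to 3 points and 3 to 5 points. For DoR with a true median of 12 months, the gap is about 3 points at 10% and 7 at 20%, or 1 to 2 and 3 to 5 with deaths. The true share is not in the documents, so the actual effect could be smaller or larger. No shift in the medians is claimed, and the primary ORR does not depend on this choice.

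**What to change.** 1. State in the SAP that 6.14.2 and Table 13 give the main rule, in line with protocol 10.6.2.2, and that it covers PFS, DoR, TTP and EFS under IRC and, where analysed, INV.
2. Delete the clinical-deterioration bullet in 6.9, or confine it to a labelled sensitivity analysis.
3. Keep the dating sentence in 10.2.6, limited to non-radiological progression that meets Cheson criteria.
4. Add one sensitivity analysis that changes only this rule, counting clinical progression as an event on the discontinuation date, for PFS, DoR and TTP under IRC and INV.
5. Add the INV clinical-progression row to the alternative-censoring table in 20.9.

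The cost is SAP wording and one extra sensitivity run. Its estimate may look less favourable and may count some tumour flare as progression, which the report should say.
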